## APPENDIX C. PROTOCOL AMENDMENT SUMMARY OF CHANGES

Document	Date
Amendment (Version) 1:	30 AUG 2016
Amendment (Version) 2:	09 NOV 2016
Amendment (Version) 3:	23 FEB 2017
Amendment (Version) 3-CAN:	12 DEC 2017
Amendment (Version) 4:	05 NOV 2019

### Amendment 4 (05 NOV 2019)

**Overall Rationale for the Amendment:** The primary purpose of this amendment is to reduce Protocol-required procedures for subjects who remain on study treatment. Subjects should be monitored per the standard of care for their condition as determined by the investigator.

1. **Synopsis; Section 4.1, Overall Study Design; Section 6, Study Assessments (including new Table 6 and Table 7); Section 7, Conduct of Study Assessments and Procedures; Section 7.3.1.1, Prior and Concomitant Medications and Procedures; Section 7.4, Safety Assessments; Section 7.4.1, Adverse Events; Section 7.4.5, Laboratory Assessments; Section 7.5.1, FDG-PET or Combined PET-CT; Section 7.5.2, Computed Tomography Scan or Magnetic Resonance Imaging; Section 7.8.1, Administration of Study Drug; Section 7.8.2, Distribution of Subject Reminder Cards**

**Description of change:** The sections were updated to include information on reduced Protocol-required assessments for subjects who are ongoing in the study.

**Rationale for change:** To reduce the burden of unnecessary procedures for the ongoing remaining subjects and the sites.

2. **Synopsis**

**Description of change:** The coordinating PI for the study was added ( [REDACTED] MD, [REDACTED] ).

**Rationale for change:** To identify the study's coordinating PI.

3. **Section 1.3, INCB050465**

**Description of change:** Added a statement to refer to the IB for current information on INCB050465.

**Rationale for change:** The IB has been updated and is a better source for this information.

4. **Section 4.6, Study Termination**

**Description of change:** Statement added indicating that upon study closure, subjects who are still receiving study treatment will have the option to transition to Study INCB 50465-214, in which they may continue to receive study treatment.

**Rationale for change:** To include a crossover option for subjects to continue treatment after study closure.

5. **Section 7.4.1, Adverse Events; Section 8.1.2, Reporting; Section 8.3.2, Reporting**

**Description of change:** Serious adverse events (SAEs) and adverse events leading to discontinuation from study treatment will be collected by the sponsor.

**Rationale for change:** Collection of all SAEs and AEs leading to discontinuation is sufficient for safety monitoring of the study treatment at this point in the study.

6. **Incorporation of administrative changes.** Other minor, administrative changes have been incorporated throughout the Protocol and are noted in the redline version of the amendment.

### **Amendment 3-CAN (12 DEC 2017)**

**Overall Rationale for the Amendment:** To remove a criterion for study treatment discontinuation per Health Canada's request.

#### **1. Section 5.5.1, Criteria for Study Treatment Discontinuation**

**Description of change:** The following bullet has been deleted from Section 5.5.1:

- If a subject is found not to have met eligibility criteria, then the medical monitor and investigator will collaborate to determine whether the subject should be withdrawn from the study.

**Rationale for change:** To meet Health Canada requirements.

### **Amendment 3 (23 FEB 2017)**

#### **Overall Rationale for the Amendment:**

The primary purpose of this amendment is to address changes requested by the European Regulatory Agency.

This amendment includes the changes to Protocol INCB 50465-202 Amendment 2 (09 NOV 2016) summarized below. A redline version of the amendment depicting updated and previous text is also provided.

1. **Synopsis; Section 1.4, Study Rationale; Section 3.1, Subject Inclusion Criteria**

**Description of change:** Change the minimum number of allowed prior systemic therapies from 1 to 2 and provide types of prior therapies.

**Rationale for change:** Requested by European Regulatory Agency.

2. **Synopsis; Section 1.5, Potential Risks and Benefits of the Treatment Regimen; Section 5.2.2, Supply, Packaging, and Labeling; Section 5.6.1, *Pneumocystis Jirovecii* Prophylaxis**

**Description of change:** Require that all subjects receive prophylaxis against *Pneumocystis jirovecii* pneumonia.

**Rationale for change:** Requested by European Regulatory Agency.

3. **Section 1.4, Study Rationale**

**Description of change:** The dose rationale was moved from Section 1.5, Potential Risks and Benefits of the Treatment Regimen, to Section 1.4, Study Rationale.

**Rationale for change:** To relocate the dose rationale to the appropriate section of the Protocol.

4. **Section 1.5, Potential Risks and Benefits of the Treatment Regimen**

**Description of change:** A paragraph was added stating that subjects should avoid sun/ultraviolet light.

**Rationale for change:** Requested by European Regulatory Agency.

5. **Section 3.1, Subject Inclusion Criteria; Section 6, Study Assessments (Table 5)**

**Description of change:** The amount of time that men should avoid fathering a child was increased to 93 days in inclusion criterion 8c; an administrative error was corrected by removing the pregnancy test on Day 1 in inclusion criterion 8b. Pregnancy test for women of childbearing potential was added at each 3-week visit in Table 5.

**Rationale for change:** Requested by European Regulatory Agency.

6. **Section 3.2, Subject Exclusion Criteria**

**Description of change:** Exclusion criterion 13 was modified to exclude subjects that had exposure to a live vaccine within 30 days of study drug administration.

**Rationale for change:** Requested by European Regulatory Agency.

7. **Section 3.2, Subject Exclusion Criteria (criterion 14); Section 6, Study Assessments (Tables 5 and 6); Section 7.4.5.4, HIV Screening Test**

**Description of change:** Require that subjects enrolled outside the United States have an HIV test at screening.

**Rationale for change:** Requested by European Regulatory Agency.

8. **Section 5.4.1, Criteria and Procedures for Dose Interruptions and Reductions of INCB050465 (Table 2)**

**Description of change:** Provide guidance that all subjects with Grade 3 ANC ( $< 1.0 \times 10^9/L$ ) should have INCB050465 administration interrupted.

**Rationale for change:** Requested by European Regulatory Agency.

9. **Incorporation of administrative changes.** Other minor, administrative changes have been incorporated throughout the Protocol and are noted in the redline version of the amendment.

## **Amendment 2 (09 NOV 2016)**

### **Overall Rationale for the Amendment:**

The primary purpose of this amendment is to change the dose of INCB050465.

This amendment includes the changes to Protocol INCB 50465-202 Amendment 1 (30 AUG 2016) summarized below. A redline version of the amendment depicting updated and previous text is also provided.

1. **Synopsis; Section 1.4, Study Rationale; Section 4.1, Overall Study Design; Section 5.2.1, Description and Administration**

**Description of change:** The dose of INCB050465 has been changed from 30 mg once daily to 20 mg once daily for 8 weeks followed by 20 mg once weekly.

**Rationale for change:** As of 02 SEP 2016, among all subjects (n = 46) in study INCB 50465-101, 11 (24%) have discontinued study drug due to an adverse event (AE). Among the subjects with an objective response (n = 20), 7 (35%) discontinued study treatment due to an AE. The dose has been changed in an effort to reduce the frequency of AEs that lead to study drug discontinuation.

2. **Synopsis; Section 3.1, Subject Inclusion Criteria**

**Description of change:** Inclusion criterion 1 was modified to allow only subjects aged 19 years or older to enroll in South Korea.

**Rationale for change:** The legal adult age in South Korea is 19 years.

3. **Section 1.3, INCB050465**

**Description of change:** Safety and efficacy data have been updated based on a data cut of 02 SEP 2016.

**Rationale for change:** These changes were made to provide the most recent emerging data to support the need for a dose change and the new dose rationale.

4. **Section 1.5, Potential Risks and Benefits of the Treatment Regimen**

**Description of change:** The potential risks and benefits of the treatment regimen were updated based on the 02 SEP 2016 data cut, and the dose rationale was provided.

**Rationale for change:** The changes were made to provide a current interpretation based on the most recent data. The dose rationale was changed to support the new dose.

5. **Section 5.4, Treatment Interruptions and Adjustments**

**Description of change:** Table 2 (Guidelines for Interruption and Restarting Study Drug) and Table 3 (Dose Levels for INCB050465) were updated, and the term "immune-related adverse event" was defined.

**Rationale for change:** New guidance was provided for AEs that have caused treatment discontinuation in Study INCB 50465-101 to assist physicians manage these AEs. The term "immune-related adverse event" was defined so investigators can consistently answer the following question in the eCRF: "Is this event an immune-related adverse event?"

6. **Section 6, Study Assessments (Table 4: Schedule of Assessments)**

**Description of change:** The frequency of drug dispensing was altered.

**Rationale for change:** Because the dose schedule changed from daily to weekly at Week 9, the dose dispensing schedule was changed to reduce the amount of drug that would otherwise be discarded.

7. **Section 8.4, Adverse Events of Special Interest**

**Description of change:** Rash  $\geq$  Grade 2 was added to the list of adverse events of special interest, and diarrhea was changed to  $\geq$  Grade 2.

**Rationale for change:** Rash was added because this is an AE that has led to study treatment discontinuation and has occurred with some frequency in Study INCB 50465-101. The change in diarrhea reporting was made to reduce the amount of expedited reporting for this event.

8. **Incorporation of administrative changes.** Other minor, administrative changes have been incorporated throughout the Protocol and are noted in the redline version of the amendment.

## **Amendment 1 (30 AUG 2016)**

### **Overall Rationale for the Amendment:**

The primary purpose of this amendment is to fulfill a request from the FDA to 1) add an Independent Data Monitoring Committee and 2) Conduct an interim analysis for futility in Group A.

This amendment includes the changes to Protocol INCB 50465-202 (26 MAY 2016) summarized below. A redline version of the amendment depicting updated and previous text is also provided.

**1. Synopsis; Section 4.1, Overall Study Design; Section 9.2, Selection of Sample Size; Section 9.6, Interim Analysis**

**Description of change:** An interim futility analysis has been added. The analysis is planned when the first 40 subjects in Group A have been treated and have been evaluated for response or have permanently discontinued study treatment because of disease progression, withdrawal of consent, or death. Group A of the study will be terminated for futility if  $\leq 13$  of the 40 subjects have responded (ie, complete response [CR]/complete metabolic response [CMR] or partial response [PR]/partial metabolic response [PMR]) based on assessments provided by the independent review committee; otherwise the study will continue. A timely assessment of response will be performed to avoid the risk of overenrollment. No formal futility analysis will be conducted for Group B. Section 9.2 (Selection of Sample Size) was updated to be consistent with the numbers used in the added interim analysis.

**Rationale for change:** Requested by the FDA.

**2. Synopsis; Section 4.1, Overall Study Design; Section 4.6, Study Termination; Section 8.7, Independent Data Monitoring Committee; Section 9.5, Analyses for the Independent Data Monitoring Committee**

**Description of change:** An independent Data Monitoring Committee (IDMC) was included in the study to review safety and perform the futility analysis.

**Rationale for change:** Requested by the FDA.

**3. Synopsis; Section 2, Study Objectives and Endpoints**

**Description of change:** The primary objective was updated to clarify that efficacy will be assessed in terms of objective response rate (ORR) in Group A, and study endpoints were updated to indicate Group A or Group B where applicable.

**Rationale for change:** For clarity and to make the objectives and endpoints consistent.

**4. Synopsis; Section 2.2, Study Endpoints; Section 4.1, Overall Study Design; Section 5.5.1, Criteria for Study Treatment Discontinuation; Section 6, Study Assessments; Section 7.5.3, Bone Marrow Examination; Section 7.5.5, Response Criteria – The Lugano Classification; Section 9.4.1, Efficacy Analyses**

**Description of change:** Complete response (CR), partial response (PR), and progressive disease (PD) were changed throughout the document to complete response/complete metabolic response (CR/CMR), partial response/partial metabolic response (PR/PMR), and progressive disease/progressive metabolic disease (PD/PMD).

**Rationale for change:** The change was made to be consistent with the endpoints of the Lugano Criteria, which are being used to evaluate the disease assessments.

5. **Section 5.4.1, Criteria and Procedures for Dose Interruptions and Reductions of INCB050465 (Table 2); Section 5.4.2, Supportive Care Guidelines for Diarrhea/Colitis; Section 11, References**

**Description of change:** Guidance for management of diarrhea and colitis was added, and guidance for ALT/AST elevation and Grade 3 toxicities was modified.

**Rationale for change:** To support investigators whose subjects experience diarrhea/colitis, which has been observed in the ongoing INCB050465 Phase 1 study.

8. **Incorporation of administrative changes.** Other minor, administrative changes have been incorporated throughout the Protocol and are noted in the redline version of the amendment.

WBC	white blood cell
WHO	World Health Organization

1. INTRODUCTION

This is a Phase 2, multicenter, international, open-label study designed to evaluate the safety and efficacy of INCB050465 20 mg QD for 8 weeks followed by 20 mg QW. The study drug will be administered orally to subjects with relapsed or refractory DLBCL. The study consists of 2 groups: Group A and Group B. In Group A, 100 subjects who were not previously treated with a BTK inhibitor (eg, ibrutinib) will be enrolled. In Group B, up to 20 subjects who were previously treated with a BTK inhibitor (eg, ibrutinib) will be enrolled.

Section 1 of the Protocol provides a detailed description of the investigational product, target patient population, rationale for doses to be examined, and potential risks and benefits of treatment with INCB050465.

The purpose of this SAP is to provide details of the statistical analyses that have been outlined in the Study INCB 50465-202 Protocol. The scope of this plan includes the interim and final analyses that are planned and will be executed by the Department of Biostatistics or designee.

2. STUDY INFORMATION, OBJECTIVES, AND ENDPOINTS

2.1. Protocol and Case Report Form Version

This SAP is based on INCB 50465-202 Protocol Amendment 3 dated 23 FEB 2017 and CRFs approved 16 NOV 2017. Unless superseded by an amendment, this SAP will be effective for all subsequent Protocol amendments and CRF versions.

2.2. Study Objectives

2.2.1. Primary Objective

• To assess the efficacy of INCB050465 in terms of ORR in subjects with relapsed or refractory DLBCL in Group A.

2.2.2. Secondary Objectives

- To assess the DOR in Group A.
- To assess PFS in Group A.
- To assess OS in Group A.
- To characterize the safety of INCB050465 in Group A and Group B.

2.3. Study Endpoints

2.3.1. Primary Endpoint

ORR in Group A, defined as the percentage of subjects with a CR/CMR or PR/PMR
as defined by revised response criteria for lymphomas (Cheson et al 2014), as
determined by an IRC.

2.3.2. Secondary Endpoints

[figure not shown]
- DOR in Group A, defined as the time from first documented evidence of CR/CMR or PR/PMR until disease progression or death from any cause among subjects who achieve an objective response, as determined by radiographic disease assessment provided by an IRC.
- PFS in Group A, defined as the time from the date of the first dose of study drug until the earliest date of disease progression, as determined by radiographic disease assessment provided by an IRC, or death from any cause.
- OS in Group A, defined as the time from the date of the first dose of study drug until death by any cause.
- Safety as measured by clinical assessments, including vital signs and physical examinations, 12-lead ECG, chemistry and hematology laboratory values, and AEs.

3. STUDY DESIGN

This is a Phase 2, multicenter, international, open-label study designed to evaluate the safety and efficacy of INCB050465 20 mg QD for 8 weeks followed by 20 mg QW. The study drug will be administered orally to subjects with relapsed or refractory DLBCL (see Figure 1). The study consists of 2 groups: Group A and Group B. In Group A, 100 subjects who were not previously treated with a BTK inhibitor (eg, ibrutinib) will be enrolled. In Group B, up to 20 subjects who were previously treated with a BTK inhibitor (eg, ibrutinib) will be enrolled. Subjects will be evaluated for ORR by an IRC and followed for DOR, PFS, and OS. Subjects may receive treatment until disease progression, death, unacceptable toxicity, or consent withdrawal. An interim futility analysis is planned when the first 40 subjects in Group A have been treated and have been evaluated for response or have permanently discontinued study treatment because of disease progression, withdrawal of consent, or death. Group A of the study will be terminated for futility if \leq 13 of the 40 subjects have responded (ie, CR/CMR or PR/PMR) based on assessments provided by the IRC; otherwise the study will continue. No formal futility analysis will be conducted for Group B.

Figure 1: Study Design

3.1. Randomization

Not applicable.

3.2. Control of Type I Error

There will not be any statistical comparison between the 2 groups. Within each group, 2-sided 95% CIs will be reported for all analyses when appropriate.

Within each group, no adjustment for alpha-spending is considered, as there are no plans to stop the study early for overwhelming efficacy. An IDMC will be assembled to monitor safety data and study conduct on a regular and ongoing basis during the study. The IDMC will also be charged with evaluating interim futility results. See Section 9 for details regarding interim analyses conducted in this study.

3.3. Sample Size Considerations

The study will enroll 100 subjects into Group A. If the true ORR is 0.50, then there is approximately 90% probability of observing the lower bound of the 95% CI of the ORR \geq 35%.

The study will enroll up to 20 subjects in Group B.

3.4. Schedule of Assessments

Refer to Protocol Amendment 3 dated 23 FEB 2017 for a full description of all study procedures and assessment schedules for this study.

4. DATA HANDLING DEFINITIONS AND CONVENTIONS

4.1. Scheduled Study Evaluations and Study Periods

4.1.1. Day 1

Day 1 is the date that the first dose of study drug (INCB050465) is administered to the subjects.

4.1.2. Study Day

If a visit/reporting date is on or after Day 1, then the study day at the visit/reporting date will be calculated as

Day # = (Visit/Reporting Date - Day 1 date + 1).

If the visit/reporting date is before Day 1, then the study day at the visit/reporting date will be calculated as

Day # = (Visit/Reporting Date - Day 1 date).

A study day of -1 indicates 1 day before Day 1.

4.1.3. Baseline Value

Baseline is the last nonmissing measurement obtained before the first administration of INCB050465, unless otherwise defined.

When scheduled assessments and unscheduled assessments occur on the same day and time of the assessment or time of first dose is not available, use the following convention to determine baseline:

- If both a scheduled and an unscheduled visit are available on the day of the first dose and the time is missing, use the scheduled assessment as baseline.
- If all scheduled assessments are missing on the day of the first dose and an unscheduled assessment is available, use the unscheduled assessment as baseline.

4.1.4. Handling of Missing and Incomplete Data

In general, values for missing data will not be imputed unless methods for handling missing data are specified in this section or relevant sections.

When calculating time since diagnosis/transformation of cancer, partial diagnosis/transformation date will be handled as follows:

- If only the day is missing, then the imputed day will be the first of the month.
- If both the month and day are missing, then the imputed day and month will be 01 JAN.
- No imputation will be done if the date is completely missing.

Missing or partial date of last dose will be handled as follows:

- If only the day is missing, then the imputed date of the last dose will be the earlier date of the first day of the month or the date that the subject discontinued treatment.
- Otherwise, the date that the subject discontinued treatment will be used as the date of the last dose.

When calculating DOR, PFS, and OS, partial dates will be imputed as follows:

- If mmyyyy for the last contact known alive date = mmyyyy for the death date, then the death date will be set to the day after the last contact known alive date.
- If mmyyyy for the last contact known alive date < mmyyyy for the death date, then the death date will be set to the first day of the death month.
- Otherwise, the partial death date will not be imputed.

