**Table 1: Description and Administration**

Compound name	INCB050465
Dosage Strengths	5 mg and 20 mg
Form	Tablet
Active compound	INCB050465
Route of administration	Oral
Dose and Regimen	20 mg QD for 8 weeks followed by 20 mg once weekly
Instructions	INCB050465 will be taken orally with water in a fasted state except on mornings of [REDACTED] clinic visits (see Table 11). Subjects should refrain from food consumption for 2 hours before and 1 hour after administration of INCB050465.

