6.4. Exposure

For subjects in the safety population, exposure to INCB050465 will be summarized descriptively as the following:

- **Duration of treatment with INCB050465 (days):** Date of last dose of study drug date of first dose of study drug + 1.
- Duration of treatment with INCB050465 for initial QD schedule (days): Date of last dose of study drug during initial QD schedule date of first dose of study drug + 1.
- **Duration of treatment with INCB050465 for QW schedule (weeks):** Ceiling of [(date of last dose of INCB050465 during QW schedule date of first dose of INCB050465 during QW schedule + 1) / 7].
- Average reported daily dose of INCB050465 for initial QD schedule (mg/day): Total reported INCB050465 dose taken during initial QD schedule (mg) / duration of treatment with INCB050465 for initial QD schedule (days).

- Average reported weekly dose of INCB050465 for QW schedule (mg/week): Total reported INCB050465 dose taken during QW schedule (mg) / duration of treatment with INCB050465 for QW schedule (weeks).
- **INCB050465 dose modifications:** Number of subjects who had INCB050465 dose reduction and interruption will be summarized for initial QD schedule, QW schedule, and overall.

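### A last-dose date missing only its day is in practice set to the first of the month with no floor at the first dose, so exposure is never lengthened, usually shortened, and can come out zero or negative

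*SAP*

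**What the plan says.** SAP 4.1.4 has two rules for a missing or partial last-dose date. If only the day is missing, the imputed date is "the earlier date of the first day of the month or the date that the subject discontinued treatment". In every other case the discontinuation date stands in: "Otherwise, the date that the subject discontinued treatment will be used as the date of the last dose". Neither rule refers to the first-dose date or to any dosing date already recorded.

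SAP 6.4 uses the last-dose date in duration of treatment, which is last dose minus first dose plus 1. The QD and QW schedules have durations of their own, built from the last dose within each schedule, and these are the denominators of the dose averages. The daily average is "Total reported INCB050465 dose taken during initial QD schedule (mg) / duration of treatment with INCB050465 for initial QD schedule (days"). The weekly average is formed in the same way over QW weeks, with the duration in weeks rounded up. SAP 6.4 does not say how the total reported dose is obtained when the end date is partial.

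The schedule is "20 mg QD for 8 weeks followed by 20 mg once weekly" (Protocol Table 1). Exposure and compliance are reported in SAP Table 3.1.

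**The concern.** Taking the earlier of two dates makes sense as a cap, and a cap works only on a date that might be too late. The first of the month is already the earliest day on which the last dose could have fallen. Treatment is not normally discontinued in a month before the last dose, so the discontinuation date has no effect unless the records conflict.

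The two rules also sit oddly together. A subject whose month and day are both missing receives the discontinuation date, and a subject whose month is known receives the first of that month. Knowing less can therefore give a longer exposure.

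At stake are treatment duration, which would be understated and in some subjects impossible, and possibly the average doses. If the plan is silent when a negative duration appears, someone must patch it during programming.

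**Working it through.** The plan states no figure for this rule, so there is nothing to reproduce. The check applies the SAP 4.1.4 rule and the SAP 6.4 duration to example dates in 2017.

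**1. Loss of exposure.** If the true last dose is on day k of its month, and discontinuation is on or after it, the imputed date is day 1 and the loss is k - 1 days. That is 0 when k = 1 and 30 when k = 31. With last-dose days spread evenly over a 365-day year, the mean loss is

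(7 × 465 + 4 × 435 + 378) / 365 = 5373 / 365 = 14.7 days,

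where 465, 435 and 378 are the sums of 0 to 30, 0 to 29 and 0 to 27 for months of 31, 30 and 28 days. The loss is zero on 12 of 365 days (3.3%). A full enumeration crossed every 2017 start date with every true length of 1 to 56 days, which is 20,440 combinations. Discontinuation was set 0, 1, 7 or 14 days after the last dose. At each lag, exposure was shortened in 96.7% of combinations, unchanged in 3.3% and lengthened in none.

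**2. Impossible durations.** If first and last dose share a month and the first dose is on day d, then

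imputed duration = 1 - d + 1 = 2 - d.

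- First dose 2 March: 0 days.
- First dose 10 March, true last dose 28 March: -8 days, against a true 19.
- First dose on the 31st: -29 days, the worst case.

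How often this happens among subjects *with* a day-missing date depends on how long treatment lasts. Assume evenly spread start dates and exponentially distributed treatment length. With the 104-day median of the Phase 1/2 study (Protocol 1.3), about 9% of such subjects get an imputed last dose before their first dose. With a mean of about 9 months, the treatment period expected in the Protocol Synopsis (taken as 270 days), it is about 5%. Neither is an expected rate for the trial, because the documents do not say how many dates will be partial.

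The QW duration has the same weakness against its own start. With a first QW dose on 7 March and a true last dose on 28 March, the true duration is 22 days, or 4 weeks. Imputed to 1 March it is -5 days, which rounds up to 0 weeks and leaves the weekly average undefined.

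**3. Average dose.** Assume full adherence at the scheduled dose.

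| Case | Dose taken | True duration | Imputed duration | Average, dose total not cut | Average, dose total cut at imputed date |
|---|---|---|---|---|---|
| QD, 10 January to 28 February | 50 × 20 = 1000 mg | 50 days | 23 days | 1000 / 23 = 43.5 mg/day | 20.0 mg/day |
| QD, 10 January to 1 February | 23 × 20 = 460 mg | 23 days | 23 days | 20.0 mg/day | 20.0 mg/day |
| QW, 7 March to 30 May | 13 × 20 = 260 mg | 13 weeks | 8 weeks | 260 / 8 = 32.5 mg/week | not calculated |

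The inflation appears only if the dose total is summed without regard to the imputed end date. For the daily average, the rule clearly reaches only subjects who stop during the QD phase. In a subject who has moved to weekly dosing, the last QD dose is not the last dose of study drug.

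**The case against.** The strongest reply is that this hardly matters. Drug accountability and tablet counts (Protocol 5.3), the end-of-treatment visit (5.5.2) and data verification (10.3) should make a day-missing last dose uncommon. ORR, DOR, PFS and OS do not use the last-dose date. The TEAE definition has no last-dose cut-off, and compliance (SAP 6.5) divides by prescribed dose. All of that stands, and it limits the point to descriptive exposure.

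A second reply is that SAP 4.1.4 also uses the first of the month for partial diagnosis dates and some partial death dates, and that the earliest date cannot overstate exposure. As a choice of direction, that is defensible. It does not excuse a date before the first dose. When the months match, the death-date rule in the same section sets death to the day after the subject was last known alive. The last-dose rule has no such safeguard.

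A third reply is that imputing to month end or discontinuation reverses the bias. It does, within limits: for 10 to 28 March with discontinuation recorded 7 days after the last dose, it gives 22 days against a true 19.

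A reader might infer that every affected subject loses exposure, or that average doses are bound to be inflated. The documents support neither. A true last dose on the 1st loses nothing, dates missing more than the day follow the other rule, and the inflation depends on a dose total whose derivation the SAP leaves open.

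**Conclusion.** The point holds as a minor, easily corrected defect in a stated rule. For dates missing only the day, and with discontinuation not recorded in an earlier month, the result is always the first of the month. It can precede the first dose, and nothing else in the SAP prevents that. The 0 to 30 day range and the 2 - d formula follow directly from the rule; the 14.7-day mean needs evenly spread dates. Average doses above 20 mg are possible, not established. The number of affected subjects is unknown and probably small, and no efficacy result or decision rule is touched.

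**What to change.** In SAP 4.1.4, when only the day is missing, impute the earlier of the last day of the month and the treatment discontinuation date, and never a date before the first-dose date or the last *complete* dosing date on the CRF. The word complete matters, because the partial date may come from the same form. For the QW duration it is the last complete dosing date that protects, since the first dose of study drug can be weeks before the QW schedule starts. In SAP 6.4, state that the dose total and the duration use the same end date.

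The cost is one sentence in each section and a line of derivation code. The downside should be stated with it: when discontinuation is recorded after the last dose, exposure is overstated by at most the gap to month end or to discontinuation, whichever is shorter. For 10 January to 14 February with discontinuation 7 days later, that gives 43 days against a true 36. If the sponsor prefers to keep the first of the month, the minimum change is to add the floor at the first dose or last complete dosing date.
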